Title:

A randomized, double blind, crossover trial comparing fexofenadine to placebo for the treatment of proton pump inhibitor (PPI) refractory gastroesophageal reflux symptoms

Principal Investigator:

[name]

Supervisory Faculty:

[name]

Other Investigators:

[name]; [name]; [name]; [name]

Funding Source:

Stanford University Department of Gastroenterology Esophageal Seed Grant

Aims:

1. Evaluate the efficacy of fexofenadine in the treatment of proton pump inhibitor (PPI) refractory gastroesophageal reflux disease (GERD).
2. Evaluate side effects and tolerability of fexofenadine in a population of treatment refractory GERD patients.

Background and Rationale:

About 18-28% of North American adults have GERD at least once per week (1). Proton pump inhibitors (PPIs) are common treatments, but as many as 60% of GERD subjects experience heartburn despite use (2-6). While residual acid exposure may play a role in some patients, PPIs are quite effective at reducing acid reflux (7-10). Another possible explanation is that the persistent heartburn represents neuropathic pain. One potential mechanism includes activation of transient receptor potential channel vanilloid subfamily member 1 (TRPV1) (11). These channels are known to be activated by mechanoreceptors (11) and balloon distension can induce heartburn in healthy volunteers (12). In addition, expression of TRPV1 messenger RNA and protein in esophageal mucosa from subjects with both erosive and non-erosive GERD was significantly higher than that in from health subjects (12).

Recently, histamine has been found to sensitize TRPV1 in rectal biopsy specimens from subjects with irritable bowel syndrome via an action mediated by histamine H1-receptors (13). Moreover, in subjects with irritable bowel syndrome, a histamine H1-receptor antagonist reduced visceral hypersensitivity and abdominal pain and increased symptom relief (13).

Fexofenadine is a histamine H1-receptor antagonist that is available over the counter for relief of allergy symptoms. It has a good safety profile and is generally well tolerated (14, 15). We propose to examine the ability of Fexofenadine to relieve heartburn in GERD subjects who experience heartburn or acid regurgitation despite treatment with a PPI.

Significance:

Minimal therapy exists for PPI-refractory GERD, despite being a very common disorder. If positive this trial will potentially add a valuable, safe, and widely available agent for adjunctive therapy.

Research Plan:

Study Design: Randomized, prospective, placebo-controlled, crossover trial

Population: PPI refractory GERD patients with at least 3 episodes of heartburn or reflux per week

Study Sites:

- Stanford Healthcare

Inclusion Criteria:

- Men and women aged >18.
- A minimum 6-month history of heartburn and regurgitation, as their main GERD symptoms.
- Experience at least 3 days with episodes of heartburn or regurgitation while on PPI therapy during the 7 days before randomization (run in period).
- PPI trial of at least one month. If not actively on PPI therapy they must be willing to restart therapy for the trial (a PPI that was used before).
- Need to be on PPI at least 1 week prior to starting the trial
- Female patients who are postmenopausal or using acceptable methods of birth control.

Exclusion Criteria:

- Current or historical evidence of the following GI issues:
 - Esophageal stricture
 - Primary esophageal motility disorder (per Chicago 3.0 classification), ok to have ineffective esophageal motility or fragmented peristalsis, but exclude all others (achalasia, EGJOO, jackhammer, absent peristalsis, distal/diffuse esophageal spasm)
 - Systemic sclerosis
 - Active inflammatory bowel disease
 - Zollinger-Ellison syndrome
 - Active gastric or duodenal ulcer
 - Active infectious or inflammatory conditions of the small or large intestine
 - Malabsorption syndromes
 - History of GI malignancy
 - Prior gastric or intestinal surgery
- Patients with significant co-morbidities including:
 - Decompensated cirrhosis
 - New York Heart Association class III or IV heart failure
 - Renal disease with GFR < 50
 - Pulmonary disease limiting activity or requiring oxygen
 - Malignancy
 - HIV infection
 - Significant psychiatric disease that would prevent participation in the study or accurate reporting of symptoms
 - Transplant
- Unable or unwilling to stop any anti-histamine drugs during the run in period
- Active drug or alcohol abuse
- Pregnancy or breast feeding
- Non-English speaking
- Unable or unwilling to give informed consent.
- Unable or unwilling to comply with study protocol for any reason

Intervention: Fexofenadine capsule 180 PO daily

Comparator: Identical placebo capsule

Trial Length: Total length 6 weeks: 1 week run-in, 2 weeks randomization to placebo vs fexofenadine, 1 week washout, 2 weeks crossover

Primary Outcomes: Mean percentage of GERD free days, Mean number of GERD episodes.

Secondary Outcomes: Mean GERD-HRQL questionnaire score, Mean symptoms severity score (on a scale of 0-4), side effects, mean percentage of days on which rescue medications are needed, patient medication preference.

Statistical Considerations:

Sample Size: Sample size estimation was made referencing a trial evaluating GERD patients refractory to lansoprazole 30 mg daily. Patients in this trial were then randomized to treatment with lansoprazole twice daily or esomeprazole once daily. The mean percentage of GERD free days in the twice daily lansoprazole group was 57.5% (standard deviation 34.8%) (16). For the purposes of our trial with fexofenadine, we considered an additional 50% reduction in percentage of days with symptomatic GERD as a clinically significant endpoint (or mean percentage of GERD free days of 78.75%). Using alpha = 0.05 and beta 0.8 with paired means we calculated a needed sample size of 24 patients. *Our overall goal will be to recruit 40 patients to allow room for error.*

Data Analysis: We plan to analyze all data using a paired t-test comparing response to fexofenadine to response to placebo for each individual patient, provided data has a normal distribution. If not, then paired non-parametric analysis will be used. We will look specifically at the last week of treatment as we expect the drug to take a few days to build up to maximal effect. Drug preference will be compared using Fisher's exact test. Side effects will be compiled into a table to assess for major differences between fexofenadine and placebo.

Outline of key procedures/visits:

Recruitment:

Patients with potential proton pump refractory GERD will be contacted by phone or e-mail to assess interest, or recruited during office visits. Patients presenting to GI clinics will be pre-screened for potential recruitment. The decision to offer enrolment will be up to the treating physician. If the treating physician feels further workup or treatment is needed, then this should be done prior to initiation of the trial.

Patients will complete an intake questionnaire which will be e-mailed to them via RedCap or secure e-mail, or they will complete the form in person in the office. This intake questionnaire will be reviewed by study staff to determine eligibility to start the run-in period. Prior to run in a subject ID number will be assigned, starting with 1 and increasing sequentially. If a patient presents to an office visit, they will be consented at that time with signatures. If they are contacted by phone/e-mail, they will be provided with the consent form and explanation of the study, but formal consent and signing of the consent forms will take place after the run-in period if they are candidates to continue the study (the run-in week of the study involves no intervention other than questionnaires and is minimal risk).

Run in period (1 week):

1. Patient will take proton pump inhibitor as previously prescribed.
2. Every night before bed patient will record both the number and severity (on a scale of 0-4) of the reflux episodes during the last 24 hours, and need for rescue medications (patients can only use Tums during this trial) in a diary that we provide.

3. On the last day of the period patient will fill out a GERD-HRQL questionnaire about symptoms during the last week.

We will assess by either phone or secure e-mail the number of days on which the patient had symptoms. If the patient had enough symptoms he/she will be invited to participate and to visit the office to sign consent if this was not done at an earlier time. At this point a randomization ID number will be assigned.

Office visit or phone/e-mail conversation (needs to be an office visit if consent has not been signed):

1. Study materials will be collected thus far.
2. Randomization will occur and first drug will be distributed either in person or by mail.

First randomization period (2 weeks):

1. Patient will take proton pump inhibitor as previously prescribed.
2. Patient will also take the study drug (either fexofenadine or placebo) in the morning.
3. Every night before bed patient will record both the number and severity (on a scale of 0-4) of the reflux episodes during the last 24 hours, and need for rescue medications (patients can only use Tums during this trial) in a diary that we provide.
4. On the last day of this period patient will fill out a GERD-HRQL questionnaire about symptoms during the last week.
5. On the last day of this period patient write down any side effects potentially from the drug
6. On the last day of this period patients will say if they think they received placebo or active treatment

Washout (1 week):

1. Patient will take proton pump inhibitor as previously prescribed.
2. Every night before bed patient will record both the number and severity (on a scale of 0-4) of the reflux episodes during the last 24 hours, and need for rescue medications (patients can only use Tums during this trial) in a diary that we provide.
3. On the last day of the period patient will fill out a GERD-HRQL questionnaire about symptoms during the last week.

Crossover will occur and second drug will be shipped to the patient or distributed at the office. We will touch base with the patient either by phone/in the office/or by secure e-mail at this time.

Crossover (2 weeks):

1. Patient will take proton pump inhibitor as previously prescribed.
2. Patient will also take the opposite study drug as before (either fexofenadine or placebo) in the morning.
3. Every night before bed patient will record both the number and severity (on a scale of 0-4) of the reflux episodes during the last 24 hours, and need for rescue medications (patients can only use Tums during this trial) in a diary that we provide.
4. On the last day of this period patient will fill out a GERD-HRQL questionnaire about symptoms during the last week.
5. On the last day of this period patient write down any side effects potentially from the drug.
6. On the last day of this period patients will say if they think they received placebo or active treatment
7. On the last day of this period patient will select which drug was most effective.

Office visit or phone/e-mail conversation:

1. Study materials will be collected or mailed/e-mailed to us by the patient.
2. We will ask the patient either in person or by e-mail if they have questions and check in on how they are doing from a medical standpoint.

Drug Acquisition, Storage, and Distribution:

- Drugs will be ordered in batches of 300 from Koshland pharmacy ([name], e-mail [contact], contact [name]). The capsules will look identical.
- There will be an un-blinded person ([name]) who distributes the capsules (14 each) into bottles labeled with a code 1 or 2, which corresponds to fexofenadine or placebo. The bottles will also be labeled with subject number.
- Drugs will be stored at room temperature in a locked cabinet. Storage life is 6 months.
- During distribution a different staff member will distribute the drugs based on a randomization code that contains the subject ID number and the order of the drugs the patient will receive.
- After distribution, on the same randomization sheet the staff member will fill in the patient name, and date the drug is distributed. This will be stored in the same locked cabinet as the drugs.
- The randomization code will be kept by [name]
- We will not be perusing an IND, please see below
 - The IND Regulations [21 CFR 312.2(b)] state that clinical investigation of a drug product is exempt from the requirements for an IND if all of the following apply:
 - The Drug used in the investigation is lawfully marketed in the United States.
 - The investigation is not intended to be reported to FDA in support of new indication for use or to support any other significant change in the labeling for the drug.
 - The investigation is not intended to support a significant change in the advertising of the product.
 - The investigation does not involve a route of administration or dosage level, use in a participant population, or other factor that significantly increases the risks (or decreases the acceptability of the risks) associated with the use of the drug product.
 - The investigation is conducted in compliance with the requirements for IRB review and informed consent [21 CFR parts 56 and 50].
 - The investigation is conducted in compliance with the requirements concerning the promotion and sale of drugs [21 CFR part 312.7], e.g., the drug may not be represented as safe or effective for the purposes for which it is under investigation, nor may it be commercially distributed or sold.

Withdrawal from the study:

- Patients can be withdrawn for the following reasons
 - Side effect possibly related to the study drug
 - Failed adherence to study protocol
 - Discovery that the patient no longer meets inclusion or exclusion criteria
 - Other reasons after discussion with the other investigators

Safety Data:

The side effects of fexofenadine are minimal and similar to placebo (14, 15). Some side effects that occurred similarly in both the placebo and fexofenadine group include headache, dizziness, upper respiratory tract infection, pharyngitis, rhinitis, sinusitis, nausea, dyspnea, diarrhea, and pain. Patients will be asked to list side effects at the end of each treatment period.

Expected Results:

We suspect the majority of PPI refractory patients in our study will have a component of visceral hypersensitivity given the efficacy of PPIs in reducing acid secretion. Based on prior studies showing efficacy of H1 blockers in IBS, we suspect a similar mechanism will be at play in the esophagus to reduce the sensation of GERD.

Limitations:

This is a small-scale trial and is lacking of pH/impedance data which would better help elucidate the mechanism of GERD. However, such testing would greatly increase cost and reduce patient interest in study participation.

Future Directions:

If positive, future directions include potential collaborations with industry and potential larger scale and longer trials to bring either fexofenadine or similar drugs to market for more widespread use.

Proposed Timeline:

January-February 2018: IRB approval (IRB-44650)

February-December 2018: Recruitment and clinical trial

Jan-February 2019: Data-analysis and manuscript preparation

References:

2. Sontag SJ. Rolling review: gastro-oesophageal reflux disease. *Aliment Pharmacol Ther*. 1993;7(3):293-312.
5. Miner P, Jr., Orr W, Filippone J, Jokubaitis L, Sloan S. Rabeprazole in nonerosive gastroesophageal reflux disease: a randomized placebo-controlled trial. *Am J Gastroenterol*. 2002;97(6):1332-9.

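### The antihistamine restriction covers only the run-in week, so other H1-blockers are not barred in the weeks that are analysed and could dilute the fexofenadine-placebo difference

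*Combined protocol and SAP*

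**What the plan says.** Under Research Plan, Exclusion Criteria, the protocol excludes patients who are "Unable or unwilling to stop any anti-histamine drugs during the run in period". This is the only statement about non-study antihistamines in the document.

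Trial Length gives the sequence as "1 week run-in, 2 weeks randomization to placebo vs fexofenadine, 1 week washout, 2 weeks crossover". The run-in is thus study week 1, the first treatment period weeks 2-3, the washout week 4 and the crossover period weeks 5-6. Data Analysis states "We will look specifically at the last week of treatment", which means weeks 3 and 6.

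The step lists for the two treatment periods and the washout cover the PPI, study drug (in the treatment periods), nightly diary and questionnaires. The treatment periods add side effects and a guess at the treatment received, and the last period a preference. None mentions antihistamines. The one medicine limit carried through every period is in the diary item on rescue medication: "patients can only use Tums during this trial".

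Background and Rationale describes fexofenadine as an H1-receptor antagonist that is "available over the counter for relief of allergy symptoms".

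**The concern.** The trial asks whether H1 blockade reduces reflux symptoms in patients already on a PPI. Another H1-blocker is therefore not an incidental concomitant drug, because it belongs to the same class as the active treatment. A patient taking one in the placebo period, or in both periods, would have a smaller fexofenadine-placebo difference if the trial's own hypothesis is right. The paired analysis would then lean towards no effect.

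The stop-antihistamine criterion shows that the investigators expected some candidates to be users. Patients asked to stop for the run-in are the likeliest to resume once that week is over. A patient who did so would also have qualified under one condition and been measured under another.

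The diary items listed are episodes, severity and rescue medication. Unless the diary form, which is not shown, asks for more, the extent of antihistamine use may be unknown at analysis.

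**Working it through.** **Reading the text.**

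| Element | Where | Period it covers |
|---|---|---|
| Stop antihistamines | Exclusion Criteria | Run-in (week 1) |
| Tums as the only rescue medicine | Diary item in every period | Whole trial, for reflux rescue |
| Efficacy window | Data Analysis | Weeks 3 and 6 |
| Antihistamine rule on treatment | Step lists for both treatment periods and washout | None stated |

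Where the plan limits a medicine for the whole trial, it says so and repeats it in each period. The antihistamine rule is handled differently: it names one week, and that week ends before randomisation.

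**Inputs for the illustration.**
- From Sample Size: control mean 57.5% GERD-free days, SD 34.8, target mean 78.75%, alpha 0.05 (taken as two-sided), the stated beta of 0.8 read as power 0.80, needed n 24, recruitment goal 40.
- Effect: 78.75 - 57.5 = 21.25 points.
- Assumed, not in the documents: f, the share of patients using another H1-blocker; L, the share of the contrast lost in a user; and the SD of the within-patient differences. The 34.8 is the SD of one group. Using it as the SD of differences amounts to a within-patient correlation of 0.5, because SD of differences = 34.8 × √(2(1 - correlation)).

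**Reproducing the plan's figure.** Power is taken from the noncentral t distribution with n - 1 degrees of freedom and noncentrality (effect / SD of differences) × √n. With 21.25 and 34.8, power is 0.799 at n = 23 and 0.817 at n = 24. The plan's 24 is reproduced.

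**Dilution.** Diluted effect = 21.25 × (1 - f × L). For example, with f = 20% and L = 1 it is 21.25 × 0.80 = 17.0.

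| f | L | Effect (points) | Power, n = 24 | Power, n = 40 |
|---|---|---|---|---|
| 0 | – | 21.25 | 0.82 | 0.96 |
| 10% | 1 | 19.1 | 0.73 | 0.92 |
| 20% | 1 | 17.0 | 0.63 | 0.85 |
| 30% | 1 | 14.9 | 0.52 | 0.75 |
| 10% | 0.5 | 20.2 | 0.78 | 0.95 |
| 20% | 0.5 | 19.1 | 0.73 | 0.92 |
| 30% | 0.5 | 18.1 | 0.68 | 0.89 |

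These figures hold the SD at 34.8. Adding the extra variance from mixing users and non-users lowers power slightly: at f = 20% and L = 1, to 0.61 at n = 24 and 0.83 at n = 40.

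**Dilution (f × L) that leaves exactly 80% power.**

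| Correlation | SD of differences | n = 24 | n = 40 |
|---|---|---|---|
| 0.3 | 41.2 | already below 80% (0.68) | 12.0% |
| 0.5 | 34.8 | 2.2% | 25.6% |
| 0.7 | 27.0 | 24.2% | 42.4% |

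At the base SD, 2.2% of 24 is about half a patient with full loss of contrast, and 25.6% of 40 is about 10 patients.

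**The case against.** The strongest reply is that the criterion is an entry condition, judged before randomisation, so it naturally names the run-in as the time to stop. It speaks of stopping, not pausing, and nothing tells patients they may resume. In a placebo-controlled trial of an H1-blocker, stopping for one week only would serve no clear purpose. That is a fair reading of the intent, but staff and patients act on written instructions, and the written rule has no force after week 1. The Tums line does not fill the gap, because a patient treating allergy would not take a limit on reflux rescue as a ban on allergy drugs. Exclusion or withdrawal for not following the protocol does not help either, since there is no on-treatment rule to break.

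The intake questionnaire and diary form are not shown and could contain such an instruction or question. This stands as a limit on the claim about recording.

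The size is assumed throughout. The documents give no rate of use. Occasional tablets, or use in one period only, need not remove all contrast, and patients unable to do without antihistamines are screened out by the criterion itself. This also stands: the upper rows of the illustration are possibilities, not predictions.

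Any minimum sample size absorbs almost no dilution, so the n = 24 column says little about antihistamines in particular, and the goal of 40 gives real room. That is correct at the base SD. But the extra patients are meant as a general margin and must also cover dropouts and missing diaries. With 32 evaluable patients, for instance, the tolerable dilution at SD 34.8 is about 16%.

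Finally, the bias runs towards the null and does not create a false claim of benefit. True, but a false null is a serious loss for a trial whose purpose is to detect an effect.

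**Conclusion.** The concern holds. As written, the antihistamine restriction does not reach the weeks on which efficacy is judged, and use of same-class drugs in those weeks could shrink the primary contrast without being recorded. The text gap is certain; the size of its effect is not. At the SD that reproduces the plan's n, 40 evaluable patients keep 80% power up to about 26% dilution, and 24 keep it only up to about 2%. With a within-patient correlation of 0.3, the margin at 40 falls to 12%. All of this depends on assumed rates of use and loss of contrast. The change should be made because it is nearly free and protects the comparison the trial exists to make; the plan is not otherwise invalidated.

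A separate, minor point does not bear on this conclusion. Recruitment says that "the run-in week of the study involves no intervention other than questionnaires and is minimal risk", which is given as the reason why patients recruited by phone or e-mail may sign consent after it. That is not accurate for a patient who is asked to stop an antihistamine for the run-in.

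**What to change.** - Reword the exclusion criterion to: unable or unwilling to stop all non-study antihistamine drugs from the start of the run-in until the end of the crossover period.
- Repeat the instruction in the step list for each period, including the washout.
- Add one yes/no line on non-study antihistamine use to the nightly diary.
- Keep all patients in the primary analysis. Report any analysis excluding users as supportive only, because use occurs after randomisation and may depend on the treatment received.
- Have phone or e-mail recruits who take antihistamines sign consent before they stop.

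The cost is protocol wording and one diary line. Some patients with allergies may decline. Signing consent needs an office visit under the current plan, so the few remote recruits who take antihistamines would make that visit before the run-in instead of after it. The planned sample size does not change.

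### Two unranked primary outcomes with no success rule: if either can carry the efficacy claim, the chance of a false claim for fexofenadine is about 3.5% to 4.5% instead of 2.5%

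*Combined protocol and SAP*

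**What the plan says.** The Aims section has one efficacy aim. The Research Plan gives two primary outcomes for it on a single line, with no ranking: "Primary Outcomes: Mean percentage of GERD free days, Mean number of GERD episodes".

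Under Statistical Considerations, the Sample Size paragraph deals with GERD free days alone. It sets the target for that outcome ("we considered an additional 50% reduction in percentage of days with symptomatic GERD as a clinically significant endpoint") and then states: "Using alpha = 0.05 and beta 0.8 with paired means we calculated a needed sample size of 24 patients". This is the only place where an alpha appears. The recruitment goal is 40.

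The Data Analysis paragraph covers both primary outcomes in one sentence: "We plan to analyze all data using a paired t-test comparing response to fexofenadine to response to placebo for each individual patient". The t-test is conditional on normality; where that fails, a paired non-parametric test takes its place. On timing the paragraph adds: "We will look specifically at the last week of treatment". It does not state a significance level or sidedness, an order of testing, a division of alpha, or whether one or both primary outcomes must succeed. No other section does so.

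**The concern.** With two primary outcomes and no success rule, the plan does not prevent the efficacy aim from being declared met on whichever outcome reaches p<0.05. Both outcomes come from the same nightly diary, but they are not interchangeable. A patient who goes from six episodes a day to two improves greatly on episodes and not at all on GERD free days. There are thus two partly separate chances of a false positive, and the error of the overall claim exceeds the error of each test.

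The Future Directions section makes further trials and industry collaboration depend on a positive result, and the plan does not define what a positive result is.

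**Working it through.** **Inputs from the plan.** Reference mean 57.5% GERD free days, SD 34.8%, target 78.75%, alpha 0.05, power 80% (the plan writes beta 0.8), 24 patients needed, recruitment goal 40, two primary outcomes.

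**Assumptions.** Two-sided testing at 0.05 for each outcome. The SD of the within-patient difference is 34.8. Test statistics are approximately jointly normal. The documents give no correlation between the two outcomes, so a range is shown.

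**Step 1: reproduce the stated sample size.** Half of the symptomatic days is 0.5 × (100 − 57.5) = 21.25 points, and 57.5 + 21.25 = 78.75, as stated. For a paired t-test with difference 21.25 and SD 34.8:

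- Two-sided 0.05: power is 79.9% at n = 23 and 81.7% at n = 24, so 24 patients are needed. This matches.
- One-sided 0.05: 19 patients are needed. This does not match.

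Two-sided 0.05 is therefore the reasonable inference, although the plan does not state it. The corresponding rate for a false result in favour of fexofenadine on one outcome is 0.05 / 2 = 2.5%.

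**Step 2: error if either outcome suffices.** Let Z1 and Z2 be the two test statistics, signed so that positive favours fexofenadine, with correlation r and no drug effect on either outcome.

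- In favour of fexofenadine: 1 − P(Z1 < 1.96 and Z2 < 1.96)
- Either direction: 1 − P(|Z1| < 1.96 and |Z2| < 1.96)

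At r = 0 these are 1 − 0.975² = 4.94% and 1 − 0.95² = 9.75%. For other correlations they come from the bivariate normal distribution:

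| r (assumed) | In favour of fexofenadine (one test: 2.5%) | Either direction (one test: 5%) |
|---|---|---|
| 0 | 4.94% | 9.75% |
| 0.5 | 4.54% | 9.07% |
| 0.7 | 4.17% | 8.35% |
| 0.8 | 3.90% | 7.81% |
| 0.9 | 3.52% | 7.04% |

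Simulated paired t-tests on normal data agree with the last column. For r = 0, 0.5 and 0.8 they gave 9.6%, 9.0% and 7.9% at n = 24, and 9.8%, 9.1% and 7.9% at n = 40.

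**Step 3: ceiling.** In either direction, 9.75% is the maximum under joint normality or positive dependence. Without an assumption about dependence the bound is 0.05 + 0.05 = 10%.

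**Step 4: error under other success rules.** If both outcomes must be significant, the error cannot exceed that of either test alone, so it is at most 5%. If episodes are tested only after GERD free days is significant, a false claim when neither outcome has an effect needs a false positive on GERD free days, so the error is again at most 5%.

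**Step 5: cost of splitting alpha instead.** At two-sided 0.025 per outcome, the error in either direction is at most 0.025 + 0.025 = 5%. Power for GERD free days is 72.1% at n = 24, 79.9% at n = 28, 81.5% at n = 29 and 93.2% at n = 40. So 29 patients would be needed for 80%. Power for episodes cannot be computed, because the plan gives no inputs for it.

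**The case against.** A reader might infer that the plan carries up to a 9.75% chance of a false efficacy claim. The documents do not support that, for three reasons. First, about half of that figure is results in which fexofenadine does worse than placebo, and these cannot support the efficacy aim. In favour of fexofenadine, the error stays below 5% even at correlation 0 (4.94%). Second, 9.75% is the zero-correlation value, which is implausible for two outcomes taken from one diary. It is also a ceiling only under the dependence assumptions in the working. Third, the plan does not say that either outcome suffices. Its silence is equally compatible with requiring both, and then nothing is inflated.

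It can also be said that GERD free days is already the lead outcome. It is listed first, and it is the only one with a clinically significant target and a power calculation. This is a fair pointer to what the investigators had in mind, but it is not a rule. Sizing a trial on one outcome does not stop a claim on the other while both are called primary.

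The last argument is scale. This is a seed-grant trial that describes itself as small, and it claims an IND exemption, one condition of which is that the study is not meant to support a new indication. That stands, and it limits the weight of the point. It does not remove the need to say what success means.

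**Conclusion.** The gap is real: two primary outcomes are listed without rank, and no order, split or success rule is given. What follows is conditional. If each outcome is tested at two-sided 0.05 and either can carry the claim, the chance of a false claim in favour of fexofenadine rises from 2.5% to about 3.5% to 4.5% for correlations of 0.9 to 0.5. In either direction it rises from 5% to about 7% to 9%.

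These sizes rest on three things outside the text: the inferred two-sided level, approximate joint normality, and the assumed correlations. The absence of a success rule depends on none of them. The consequence is modest, and the change is worth making because it costs almost nothing.

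**What to change.** Before unblinding, state in the Research Plan and in Data Analysis that the percentage of GERD free days in the last treatment week is the single primary outcome, tested at two-sided 0.05. State that the number of GERD episodes in the same week is tested next, at two-sided 0.05, only if the first test is significant. GERD free days is the natural choice because the sample size was calculated on it.

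The calculated 24 patients, the goal of 40, the diary data and the paired tests do not change. The downside is that a result on episodes alone could no longer be called a primary success.

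If the investigators want to keep both outcomes as primary, a stated rule that both must be significant also controls the error, at a cost in power. So does an alpha split of 0.025 each, at the cost shown in step 5 of the working. The essential change is that one rule is written down before the data are unblinded.
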